6.2 FIDELITY

6.2.1 INTERVENTIONIST TRAINING AND TRACKING

Because the objectives of the protocol depend upon consistent administration of the NDURE intervention, the fidelity of delivery will be monitored closely. The specific duties necessary to ensure optimal administration of NDURE are detailed in the NDURE Navigator Standard Operating Procedure (SOP). The navigator, supervised by [name], will keep a tracking log with encounters (number, modality of each session), time (direct with patient, indirect to complete BRP), barriers (number, type), and BRP activity (action, outcome)⁴⁴. NDURE sessions will be audio-recorded and randomly selected sessions (20%) will be reviewed by [name] to ensure fidelity. Bi-monthly case conferences with the navigator, [name], and [name] will further ensure continued high-quality PN.

6.3 MEASURES TO MINIMIZE BIAS: RANDOMIZATION AND BLINDING

Bias will be minimized through stratified sampling and a stratified randomized permuted block design. We will use a stratified sampling approach to achieve a fixed sample size for AA patients (n=25 in each arm) to ensure that we 1) achieve racial balance between the NDURE and UC arms, and 2) oversample AA relative to their frequency in the study population. Oversampling AAs is key for the study design because of the prognostic significance of AA race with delayed PORT initiation^{6,33}. We will then use a stratified randomization scheme, with randomization at the individual patient level using a 1:1 allocation ratio. Strata will be defined by location of radiation facility (MUSC, non-MUSC) because of the known association of this variable with PORT delay^{6,33}. As such, our design balances by key potential confounders across trial arms. Patients will be randomized 1:1 to NDURE or usual care using a permuted block randomization method, with randomly selected block sizes of 2 or 4. Given the impossibility of delivering the NDURE intervention in a non-blinded fashion, allocation concealment will be non-blinded. The study statistician ([name]) will generate and implement the randomization schema and randomization list. The study coordinator will implement the randomization. Randomization errors will be handled as per the modified ITT population for the efficacy analysis (see **Section 9.3, Population for Analyses**).

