4.2 RCT OF NDURE VERSUS USUAL CARE

4.2.1 OVERALL DESIGN

We will conduct a single-site, non-blinded, parallel-group, RCT of NDURE versus usual care for the management of delays and racial disparities starting PORT in adults with surgically-managed, locally advanced HNSCC. The study is designed to test the following hypotheses: 1) NDURE will result in a lower rate of delayed PORT relative to usual care (primary objective) and 2) NDURE will result in a smaller difference in PORT delay between AA and whites relative to usual care (secondary objective). The statistical plan for this between-group design analyzes the superiority of NDURE relative to usual care, although our power analysis is calculated with $\alpha = 0.1$ and $1 - \beta = 0.8$ based on the desire to emphasize power over type I error at this early stage of development (single-site pilot RCT) to ensure follow-up on promising interventions.

Upon enrollment and completion of the baseline assessments, patients will be randomized 1:1 to NDURE or usual care using a permuted block randomization method, with randomly selected block sizes of 2 or 4. Randomization, which will occur at the individual patient level, will be stratified with a 1:1 allocation ratio with strata defined by race (white, AA) and location of radiation facility (MUSC, non-MUSC) because of the known association of these variables with PORT delay^{6,33}. Furthermore, to facilitate evaluation of PORT delay rates in racial subgroups, we will oversample AAs for a final sample size of 50 white and 25 AA patients in each arm (see details in **Section 9.4.6, Sub-Group Analyses**). Given the impossibility of delivering the NDURE intervention in a non-blinded fashion, allocation concealment will be non-blinded. The study statistician ([name]) will generate the randomization schema and

randomization list. The study coordinator will implement the randomization. Randomization errors will be handled as per the modified intention-to-treat (ITT) population for the efficacy analysis.

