5.5 STRATEGIES FOR RECRUITMENT AND RETENTION

Recruitment for the NDURE 2.0 trial will occur using a clinic-based approach from the MUSC Head and Neck Tumor Center, a high-volume academic HNSCC program at the NCI-designated Hollings Cancer Center. Research staff will use cancer center registry data, discussion with the HNSCC clinical team, and the electronic medical record (EMR) to identify patients who meet study inclusion criteria. Research staff will then review clinic rosters to identify eligible patients who are scheduled for an appointment in the Head and Neck Tumor Center. Study recruitment will be facilitated through the use of tested, structured protocols. [name] has evidenced-based strategies that have been successfully employed to recruit AA cancer patients to therapeutic trials. We will also use structured protocols from the principal investigator ([name]) and co-mentor [name], MPH. These protocols have been successfully employed and refined for clinic-based recruitment of patients with HNSCC to participate in behavioral research during treatment periods. Recruitment is expected to be enhanced by the active clinical practice of the PI. The study participants may include patients of the PI's, but will not be exclusively patients of the PI. For potential participants where the PI is not the attending physician and the potential participant has not consented to participate in research per EPIC, the attending physician for the patient will introduce the study to the potential participant. Other than the notification of the study by the attending physician for potential trial participants, the research team will not ask other clinicians to be involved in recruitment. All of the recruitment will be handled by the study coordinator and team.

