10 SUPPORTING DOCUMENTATION AND OPERATIONAL CONSIDERATIONS

10.1 REGULATORY, ETHICAL, AND STUDY OVERSIGHT CONSIDERATIONS

10.1.1 INFORMED CONSENT PROCESS

We will obtain full written Informed consent from patients enrolling in the study. Informed consent will occur via face-face discussion between one of the study team members designated to perform informed consent and the potential study participant. After describing the study and allowing the potential participants to ask any questions, we will schedule interviews with those who are eligible and interested in participating in the study. Participant will have time to read the informed consent form and HIPAA document on their own. Consents will be written in simple, easy-to-understand language and obtained on the day of enrollment by the trained study coordinator. A study team member will answer any questions about the study and participants will be asked to sign the consent and HIPAA forms. All participants will sign informed consent forms before the interview. All participants will receive a copy of their informed consent and HIPAA forms for their records. The informed consent process will take place in a private room in the Rutledge Tower Head and Neck Cancer Clinic or in a private room in the HCC. Only the

study participant will provide informed consent. Subjects will be allowed up to one week to decide whether to participate in the study.

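### No concealment of the next assignment is described, and in an open-label trial with blocks of 2 or 4 it may be known or guessed well above chance

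*Combined protocol and SAP*

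**What the plan says.** - **Concealment.** Section 4.2.1 reads: "Given the impossibility of delivering the NDURE intervention in a non-blinded fashion, allocation concealment will be non-blinded". Section 6.3 repeats that "allocation concealment will be non-blinded". The first clause is itself miswritten: the intended meaning is presumably that delivery cannot be blinded.
- **Sequence.** Sections 4.2.1 and 6.3 specify 1:1 allocation "using a permuted block randomization method, with randomly selected block sizes of 2 or 4". The block sizes are therefore in the protocol text. Nothing says they are withheld from recruiting staff.
- **Who recruits and consents.** Section 5.5: "All of the recruitment will be handled by the study coordinator and team". Section 10.1.1 says written consent is "obtained on the day of enrollment by the trained study coordinator".
- **Who implements.** Sections 4.2.1 and 6.3: "The study coordinator will implement the randomization". In the sentence before, section 6.3 says the statistician "will generate and implement the randomization schema and randomization list"; section 4.2.1 has the statistician only generate it.
- **Order of events.** Section 4.2.1: "Upon enrollment and completion of the baseline assessments, patients will be randomized 1:1 to NDURE or usual care".
- **Mechanism.** No central or web-based release, sealed envelopes or similar device is described. REDCap appears only for data capture and storage (sections 2.3.3, 10.1.3 and 10.1.9.1).

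**The concern.** Blinding and concealment are different safeguards. Blinding hides the treatment after it is assigned, and a navigation intervention cannot offer that. Concealment hides the next assignment until the patient is irrevocably entered, and any randomised trial can offer that. The plan uses the impossibility of the first to set aside the second.

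Followed as written, the only sentence on concealment leaves the next assignment unprotected. The role closest to the patient is also the role that implements the sequence. Because the trial is open-label at one site, past assignments are visible to staff and small blocks make the next one partly predictable.

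The risk is that who is approached, and when, comes to depend on the expected arm. Some judgement exists at entry: section 5.1 requires surgery and postoperative radiation to be considered likely, section 10.1.1 allows up to a week to decide, and section 5.5 expects 175 white patients at 60% accrual when 100 are needed. The Mantel-Haenszel test in section 9.4.2.2 adjusts for race and radiation facility. It cannot remove selection on other predictors of delay.

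**Working it through.** **1. The plan's own figure.** The documents give no figure for concealment or predictability. The nearest is power in section 9.2.2: 75 per arm, 45% against 25%, two-sided alpha 0.1, stated as 83%. With pooled variance under the null:
- null SE = √(2 × 0.35 × 0.65 / 75) = 0.0779
- alternative SE = √((0.45 × 0.55 + 0.25 × 0.75) / 75) = 0.0762
- z = (0.20 − 1.645 × 0.0779) / 0.0762 = 0.94, giving power of 82.7%

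The stated figure reproduces. Concealment does not enter it. The 20-point target serves below only as a yardstick.

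**2. Correct guesses.** Inputs: block sizes 2 or 4 (sections 4.2.1 and 6.3), assumed equally likely because no probabilities are given. Strategy: within a stratum, guess the arm with fewer patients so far, and toss a coin when level.
- Block of 2: 0.5 + 1 = 1.5 of 2 (75%)
- Block of 4: 0.5 + 2/3 + 2/3 + 1 = 2.833 of 4 (71%)
- Mixture: (1.5 + 2.833) / (2 + 4) = 72.2%

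Chance is 50%. Varying the block size at random does not lower this figure: every block ends level, so the guesser needs only the running imbalance.

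**3. Assignments known with certainty.** If the realised sizes are unknown, certainty arises only when a block opens with two of the same arm. It must then be a block of 4, and its last two assignments are fixed. Half the blocks are of size 4 and one third of those open this way, so the expected number per block is 0.5 × (1/3) × 2 = 1/3. Mean block length is 3, so the share is (1/3)/3 = 11.1%. If the realised sizes were known, it would be (1 + 1.333)/6 = 38.9%. If the list itself were visible, it would be 100%.

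**4. Check by simulation.** The simulated observer knows the possible sizes and all past assignments in the stratum, and makes the best guess each time.

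| Strata | Correct | Certain |
|---|---|---|
| Four (race by facility, section 4.2.1), N = 150 | 71.8% | 10.7% |
| Two (facility only), N = 150 | 72.0% | 11.0% |
| Four, N = 170 | 71.9% | 10.8% |

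That is roughly 16 certain assignments of 150, or 18 of 170. An equal facility split was assumed; with four strata and N = 150, a 49/51 split gave the same result.

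**5. Upper bound on bias.** Suppose every enrolment follows the guess: one type of patient when NDURE is expected, another when usual care is expected, with delay risks differing by a gap g. With probability c of a correct guess, the spurious arm difference is (2c − 1) × g = 0.444 × g. The documents give no value for g, so a range is assumed.

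| Assumed gap | Bias at 72.2% | Share of 20-point target |
|---|---|---|
| 5 points | 2.2 | 11% |
| 10 points | 4.4 | 22% |
| 20 points | 8.9 | 44% |

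**6. Would larger blocks help?** A block of 6 gives 4.1 of 6 correct guesses. Blocks of 4 and 6, equally likely, give (2.833 + 4.1)/10 = 69.3%. For a 10-point gap the bound falls only from 4.4 to 3.9 points.

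**The case against.** A reader might infer that the coordinator knows each coming assignment. The documents do not support that. No section gives the coordinator the list, the statistician generates it, and the garbled sentence looks more like confusion of two terms than a decision to run an open list. Nor does 72% mean the sequence is easily read: it needs an observer who tracks every stratum, and only about one assignment in nine is certain.

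Other points also count against a strong reading:
- Randomisation follows enrolment and baseline (section 4.2.1), and consecutive enrolment is planned (section 5.5).
- Holding a patient for a preferred arm is hard. Enrolling 170 over 36 months in four strata is 170/(36 × 4) = 1.2 per stratum per month. With an even facility split, 50 African American patients give 25 per stratum in 36 months, or one about every six weeks, while patients await cancer surgery. Accrual in that group needs 50 of 83 eligible patients, which leaves little room for passing anyone over.
- The delay nomogram collected at Visit 1 and the baseline comparison in section 9.4.4 would show some steering. The nomogram may equally give staff a risk estimate before assignment, and the primary test does not adjust for it.
- Section 5.5 says coordinator and team, and section 10.1.1 also mentions other team members. That one person does everything is plausible but not stated.

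All of this stands as mitigation, and it makes full steering unlikely. None of it supplies concealment. Randomising after baseline protects only if the assignment is unknown until then, and no procedure enforces consecutive enrolment.

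**Conclusion.** The point holds as a defect of the written procedure, not as evidence that assignments were or will be known. The plan states non-blinded concealment twice, describes no mechanism, places recruitment, consent and implementation in overlapping hands, and contradicts itself on who implements. The next assignment may therefore be known, if the list is visible, or guessed correctly about 72% of the time against 50%, with about 11% certain. Those figures rest on equally likely block sizes, known possible sizes and tracking within strata. They barely depend on whether there are two or four strata.

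The bias of 2.2 to 8.9 points is a ceiling, not a forecast. It assumes steering at every enrolment and a risk gap that the documents do not supply. Its direction is undetermined: holding high-barrier patients for NDURE would work against the intervention, while entering low-barrier patients when NDURE is expected would favour it.

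**What to change.** 1. Replace the sentence in sections 4.2.1 and 6.3 with: *Treatment is open-label; allocation is concealed.*
2. State that the statistician generates and holds the list. A central or electronic system, for example within REDCap if its set-up allows, releases one assignment only after consent, eligibility, baseline and stratum are recorded.
3. Withhold block sizes from recruiting staff, which means moving them out of protocol text those staff can see.
4. Reconcile who implements randomisation, so that sections 4.2.1 and 6.3 agree.
5. If randomisation has already begun, document the procedure actually used.

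The block sizes need not change: larger blocks would gain little (step 6 of the working) and would allow more imbalance in small strata. The cost is a wording amendment plus set-up, in a system already used for data capture if REDCap can serve.

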6.4 STUDY INTERVENTION/EXPERIMENTAL MANIPULATION ADHERENCE

Participants’ adherence with study procedures will be tracked by attendance at intervention visits. All study visits are mandatory to remain an active participant. Adherence to attendance at Visits 2-4 will be ascertained from the NDURE visit note authored by the navigator that is available in the EMR. Adherence to attendance at Visits 1 and 5 will be ascertained from the REDCap data collection form. Adherence to attendance at visits 1-5 will be documented in the electronic Case Report Form (eCRF).

6.5 CONCOMITANT THERAPY

N/A

6.5.1 RESCUE THERAPY

N/A

7 STUDY INTERVENTION DISCONTINUATION AND PARTICIPANT DISCONTINUATION/WITHDRAWAL

7.1 DISCONTINUATION OF STUDY INTERVENTION/EXPERIMENTAL MANIPULATION

At subject, PI, or study team member request.

7.2 PARTICIPANT DISCONTINUATION/WITHDRAWAL FROM THE STUDY

Participants are free to withdraw from participation in the study at any time upon request. The investigators will seek to minimize participant discontinuation/withdrawal from the study (see **Section 7.3, Lost to Follow-Up**) except for safety reasons.

The investigator may discontinue a participant from the study for the following reasons:

- Significant study intervention non-compliance
- Lost-to-follow up; unable to contact subject (see **Section 7.3, Lost to Follow-Up**)
- Any event or medical condition or situation occurs such that continued collection of follow-up study data would not be in the best interest of the participant or might require an additional treatment that would confound the interpretation of the study
- The participant meets an exclusion criterion (either newly developed or not previously recognized) that precludes further study participation. Specific situations in which this is expected to occur through the course of the study are:
 - 1) Patient is expected to have surgery and then decides to pursue a nonsurgical treatment (thus not undergoing curative-intent surgery at MUSC)
 - 2) Patient is expected to have surgery at MUSC and then decides to pursue treatment elsewhere (thus not undergoing curative-intent surgery at MUSC)
 - 3) PORT is expected based on the clinical TNM classification, but analysis of the pathology specimen after surgery demonstrates no indication for PORT (with or without concurrent chemotherapy) per NCCN Guidelines based on the absence of all of the following adverse features: ENE, positive margin, pT3 or pT4 primary, N1 or greater nodal disease, nodal disease in levels IV or V, PNI, or LVI

The reason for participant discontinuation or withdrawal from the study will be recorded on the eCRF. Subjects who sign the informed consent form and are randomized but do not receive the study intervention may be replaced. Subjects who sign the informed consent form, and are randomized and receive the study intervention, and subsequently withdraw, will not be replaced. Subjects sign the informed consent form, are randomized and receive at least some of the study intervention and are subsequently found to meet one of the exclusion criteria 1-3 described above, will be replaced.

7.3 LOST TO FOLLOW-UP

A participant will be considered lost to follow-up if he or she fails to return for two scheduled visits and study staff are unable to contact the participant after at least 3 attempts.

The following actions must be taken if a participant fails to return to the clinic for a required study visit:

- The site will attempt to contact the participant, reschedule the missed visit within 2 weeks, counsel the participant on the importance of maintaining the assigned visit schedule and ascertain if the participant wishes to and/or should continue in the study
- Before a participant is deemed lost to follow-up, the investigator or designee will make every effort to regain contact with the participant (where possible, 3 telephone calls and, if necessary, a certified letter to the participant's last known mailing address or local equivalent methods). These contact attempts will be documented in the participant's medical record or study file.
- Should the participant continue to be unreachable, he or she will be considered to have withdrawn from the study with a primary reason of lost to follow-up.

8 STUDY ASSESSMENTS AND PROCEDURES

8.1 ENDPOINT AND OTHER NON-SAFETY ASSESSMENT

Feasibility

NDURE Accrual Rate is defined as the proportion of eligible patients who enroll in NDURE

NDURE Completion Rate is defined as the proportion of enrolled patients who complete the baseline assessment, at least two NDURE intervention sessions, and the final follow-up assessment

Navigation Session Completion Rate is the proportion of NDURE navigation sessions completed by each individual

Navigator Caseload is the number of simultaneous cases (on-trial participants) being navigated by the NDURE navigator

Navigator Time Allocation (Direct) is the time (in minutes), that the NDURE navigator spends directly interacting with the patient to identify and address barriers to timely, equitable PORT

Navigator Time Allocation (Indirect) is the time (in minutes), that the navigator spends generating and enacting each Barrier Reduction Plan that is not directly interacting with the patient

Questionnaire Completion Rate is the proportion of pre- and post-treatment questionnaires completed by enrolled patients

Acceptability

Satisfaction with the Interpersonal Relationship with the Navigator Scale Score is defined as the total score of this 9-item measure of the satisfaction of the interpersonal relationship with the patient navigator. This reliable and validated measure^{30,31} has been widely used in prior studies of PN. The total score of the measure ranges from 9 (minimum) to 45 (maximum); higher scores represent a better outcome (greater satisfaction with the interpersonal relationship with the navigator).

Satisfaction with Logistical Aspects of Navigation Scale Score is defined as the total score of the 26-item measure of the satisfaction of the logistical aspects of PN. This reliable and validated measure³² has been widely used in prior studies of PN. The total score of the measure ranges from 0 (minimum) to 78 (maximum); higher scores represent a better outcome (greater satisfaction with the logistical aspects of navigation).

Clinical Outcomes

PORT Delay is defined as the initiation of PORT more than 6 weeks (42 calendar days) from the date of the definitive surgical resection. In situations in which the surgical management of the primary tumor and

the neck are staged (i.e. occur on two different calendar days), the date of the definitive surgery for the primary tumor will be used. In situations in which an additional surgical resection is required (e.g. re-resection of positive margins to clear residual disease), the date of the earlier (i.e. attempted definitive) surgical procedure will be used to determine the date of definitive surgical resection.

Time-to-PORT (TTP) is defined as the time, in days, between the date of definitive surgical resection to the initiation of PORT. All of the criteria used to adjudicate the date of the definitive surgical procedure described for the primary outcome measure will be applied to this measure.

Barriers to Care

Rate of barrier resolution is defined as the proportion of confirmed barriers (as determined by the navigator log) that are resolved during the NDURE intervention.

Unresolved barriers are the number of confirmed barriers (as determined by the navigator log) that are not resolved during the NDURE intervention.

Cancer Care Delivery Processes

Pre-Surgical Radiation Consultation is defined as the attendance by the patient at a consultation with a radiation oncologist (at MUSC or elsewhere) prior to surgery to discuss RT in the definitive or adjuvant setting

Pre-Radiation Therapy Dental Extractions is defined as the extraction of teeth prior to discharge from the index hospitalization for the definitive surgical procedure. Patients who are edentulous are not evaluable for this measure.

Surgery to Pathology Report <= 7 days is defined as the production of the pathology report from the definitive surgical procedure within the EMR within 7 calendar days of the definitive surgical procedure. Addenda to the pathology report at the request of the HNSCC team (e.g. tumor p16 status) are not counted in this measure.

Surgery to PORT Referral <= 10 days is defined as the placement of a referral for PORT, at MUSC or elsewhere, within 10 calendar days of the definitive surgical procedure.

RT Referral to Consult <= 10 days is defined as the evaluation of the patient at a postoperative consultation with a radiation oncologist within 10 calendar days of the referral being placed (or postoperative appointment being scheduled in cases in which care has been established and the return visit is no longer a consultation). The consultation may occur in the clinic or the hospital depending upon clinical circumstances.

RT Consult to Initiation <= 21 days is defined as the initiation of PORT within 21 calendar days of the patient being evaluated by a radiation oncologist for PORT.

Health Behavior Constructs

Care Transition Measure-15 (CTM-15) score is reported as a score out of 100 and calculated as the mean score (the summed score from each question divided by the total number of questions) with a linear transformation to 100. The CTM-15 is a validated, psychometrically sound 15-item, unidimensional measure of care transitions across the healthcare system that is consistent with the concept of patient-centeredness and useful from an organization perspective for the purpose of performance measurement and quality improvement⁴⁵. Items are rated on a 4-point Likert scale from 'Strongly Disagree' (1) to 'Strongly Agree' (4). Higher scores reflect more care integration and better care transitions.

Change from baseline in Interpersonal Support Evaluation List-12 (ISEL-12) score is defined as the change in total ISEL-12 scores from baseline. The ISEL-12 is a validated, 12-item assessment of three subscales (appraisal, belonging, and tangible)⁴⁶ that has been used to assess support in prior PN studies⁴⁷. Items are rated on a 4-point Likert scale from 'Definitely False' (1) to 'Definitely True' (4). The score is calculated by summing scores across all items (with reverse coding for items 1, 2, 7, 8, 11, 12). Scores range from 12-48. Higher scores indicate more support.

Change from baseline in Perceived Susceptibility Questionnaire score is defined as the change in the score for each of the two subscales relative to baseline. The Perceived Susceptibility Questionnaire is a validated 3-item perceived susceptibility subscale for mammography screening⁴⁸ that has been modified to assess perceived susceptibility for delays starting PORT after HNSCC surgery. It consists of two subscales. The first subscale consists of two questions, one assessing absolute perceived susceptibility to delays starting PORT and the other assessing relative perceived susceptibility to delays starting PORT. Items are rated on a 5-point Likert scale from 'Strongly Disagree' (1) to 'Strongly Agree' (5). The score of the subscale is calculated by summing scores across all items. Total scores for the subscale range from 2-10. Higher scores indicate greater perceived susceptibility to delays starting PORT. The second subscale is a single item assessing the cognitive evaluation of absolute perceived susceptibility to PORT delay. The item is measured as a continuous measure from 0 (no chance of delay) to 100 (guaranteed delay). Scores on this subscale range from 0-100 with higher scores indicating a greater perceived susceptibility to PORT delays.

Change from baseline in Illness Perception Questionnaire-Revised (IPQ-R) Consequences Subscale (HNSCC Modification) score is defined as the change in IPQ-R Consequences Subscale Score from baseline. The IPQ-R is a validated assessment of a patient's self-representation of the health consequences of their illness that consists of 8 separate subscales⁴⁹. The IPQ-R Consequences Subscale is easily modifiable to assess disease-specific perceived severity⁵⁰. The HNSCC Modification of the IPQ-R Consequences Subscale consists of 6 questions. Items are rated using a 5-point Likert scale from 'Strongly Disagree' (1) to 'Strongly Agree' (5). The score is calculated by summing across all items (with reverse coding for item 3). Scores range from 5 to 30. Higher scores indicate a greater degree of perceived severity of the illness.

Change from baseline in Perceived Barriers Questionnaire is a self-report measure of the presence/absence of pre-specified barriers to cancer care (yes/no). The questionnaire has been used extensively to assess perceived barriers in prior PN studies^{11,44,51,52}.

Change from baseline in Communication & Attitudinal Self-Efficacy Scale (CASE)-Cancer score is defined as the change in CASE-Cancer Score from baseline. The CASE-Cancer is a validated, psychometrically sound 12-item scale that addresses three domains of self-efficacy in cancer care (understanding and participating in care, maintaining a positive attitude, and seeking and obtaining information)⁵³. The CASE-Cancer scale has been used extensively in PN studies to measure perceived self-efficacy^{10,44,52}. Responses are on a 4-point Likert scale from 'Strongly disagree' (1) to 'Strongly Agree' (4). Higher scores indicate greater levels of self-efficacy in cancer care.

Navigator Barrier Log will measure 1) the number of barriers identified in the BRP during NDURE; and 2) the type of barrier in our modified version of existing PN logs^{11,44,51}

Covariates

Behavioral Risk Factor Surveillance Survey (BRFSS) Demographics. The BRFSS is the nation's premier health-related survey that collects data about health-related risk behaviors from US residents. The demographic section from the BRFSS will be used (in-person) to ascertain participant sex, age, race,

marital status, insurance, educational attainment, living situation, zipcode, phones for personal use, employment, and annual household income⁵⁴.

BRFSS Tobacco Use and Alcohol Consumption. The tobacco use and alcohol consumption sections of the BRFSS will be used (in-person) to characterize total cigarette exposure, current cigarette use, quit attempts, days of alcohol consumption, average drinks/day, frequency of ≥ 5 drinks, and maximum number of drinks.

Clinical and Oncologic Characteristics. Clinical characteristics will include comorbid medical conditions (as defined by the ACE-27⁵⁵, which ranks the severity of each of a patient's comorbidities from 0-3 and gives an overall comorbidity score based on the patient's highest comorbidity score for any individual type of ailment, with 3 indicating severe comorbidity) and cancer history. Oncologic characteristics will include HNSCC tumor subsite, HNSCC tumor histology, p16/human papillomavirus (HPV) tumor status, American Joint Committee on Cancer TNM Class and overall stage grouping, type of ablative surgery, type of reconstruction, treatment dates, facility of planned adjuvant therapy, and adjuvant treatment type planned (adjuvant radiation or chemoradiation).

Cultural Factor Survey Scores is reported as the total score for each of the three individual subscales. The Cultural Factor Survey is a validated, psychometrically sound questionnaire consists of three subscales assessing temporal orientation (5 items), collectivism (6 items), and religiosity (9 items)⁵⁶. Prior PN studies have used these scales to measure cultural factors⁵⁷. Items are scored on a 4-point Likert scale from 'Strongly Disagree' (1) to 'Strongly Agree' (4). Scores on each sub-scale range from 5-20 (temporal orientation), 6-24 (collectivism), and 9-36 (religiosity). Higher scores on each subscale indicate greater amounts of each of the measured construct.

PORT Nomogram is a validated risk-prediction tool to estimate a personalized pre-treatment risk of PORT delay⁵⁸.

